## 5.7 Adherence/Compliance

5.7.1 Participants will be considered compliant for purposes of evaluability of study end points if they have taken  $\geq 80\%$  of the prescribed doses of study agent.

5.7.2 The following 4 methods will be employed to monitor participants' compliance.

### 5.7.2.1 Pill Diary (Appendix B):

Upon randomization, participants will be provided with, and instructed on the use of, a pill diary. Participants will document daily dosing of the study agent on the pill diary, noting the date and time of day that the agent was taken. A "comments" column will be included in the table for participants to make a note of any missed doses, symptoms or adverse events they experience, as well as any changes to their concomitant medications. The pill diary will also include dosing instructions and important reminders about taking the study agent. Participants will be instructed to return the Pill Diary at their end of study visit. The study coordinator or designee will review the Pill Diary with the participant and both the reviewer and the participant will sign a verification of review of the Pill Diary.

#### 5.7.2.2 Pill count:

**Note: Due to a size discrepancy between the placebo and the active study agent, in order to preserve the study blind, pill counts should not be performed by a member of the study team. The count of returned tablets should be performed by the pharmacy or by an independent third party and reported to a member of the study team for documentation in the Visit Guide and compliance calculation.**

Each participant will be provided with a single bottle of study agent containing 25 doses of study agent. Participants will be instructed to bring this study agent bottle and any unused tablets back with them to their end of study visit. The number of returned doses of study agent will be subtracted from the number of doses dispensed to calculate the number of tablets that were taken during the dosing period (Day 1 – end of study dose). This number will be divided by the number of doses of study agent expected to be taken had the participant taken the study agent daily as prescribed. The resulting number x 100 will equal the % compliance.

$$\# \text{ of tablets taken} \div \# \text{ tablets prescribed for the dosing period} = \underline{\quad} \times 100 = \% \text{ compliance}$$

#### 5.7.2.3 Phone contact:

Each participant will receive an interim phone contact between their baseline and end of study visits to assess for adverse events, changes to concomitant medications and compliance with taking study agent and completion of the Pill Diary

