#### During Study Intervention

Day 5-7 Phone Contact: Review baseline symptoms and concomitant medication. Assess adverse events and compliance with study agent dosing and completion of Pill Diary. Instruct participant when they should take their dose of study agent the day prior to pioglitazone PK assessment.

Final Dose Reminder Phone Contact: 12-72 hours prior to the time the participant was instructed to take their pre-pioglitazone PK dose of study agent.

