Once a surgery date or start date for definitive radiotherapy/chemotherapy is scheduled, participants will begin taking ACTOplus met® XR (or Placebo) orally, daily for 10 to 21 doses prior to the scheduled treatment date. The day the participant begins taking agent is considered Day 1. Participants will be contacted on Day 5-7 by telephone to assess for adverse events, compliance with study agent dosing and completion of the pill diary and to review their use of concomitant medications. At this contact, the participant will be instructed what time of day they should take their dose of study agent on the day prior to the end of study collection of blood for pioglitazone trough levels. To obtain an accurate trough level, the participant should dose approximately 24 hours (and no longer than 26 hours) prior to the time that the blood draw will occur. The participant will be contacted 12-72 hours prior to this dose time to remind them of the dose timing and to NOT take a dose of study agent on the day of the blood draw. For participants who are scheduled to have their lesion surgically excised, if the surgery is re-scheduled or delayed after the participant has started taking study agent, the participant may continue to take up to 25

doses of study agent with the final dose being taken within 26 hours of the collection of the end of study tissue samples. In the event of a cancellation or postponement of surgery beyond the maximum of 26 days after the start of study agent dosing (Day 1), if the participant is willing, the tissue samples for study end point may be collected in clinic via biopsy within the day 11 to 26 window.

For all participants, the following will be obtained after 10 to 21 (up to 25 in the case of delayed surgery) days of study agent dosing and prior to performing the end of study tissue biopsies:

- FDG PET/CT scan (this is a research only scan to be performed only if the participant had a standard of care staging PET/CT prior to starting study intervention)
- CBC with differential
- Comprehensive Metabolic Panel
- Plasma sample for pioglitazone concentration
- Physical exam
- Follow-up tobacco and alcohol use assessments

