## **5.2 Study Agent Administration**

- 5.2.1 Study agent will be dispensed by a pharmacist or member of the study team to be self-administered by the participant.
- 5.2.2 One bottle of study agent containing 25 tablets will be dispensed to a participant after their eligibility has been confirmed by the CLO and they are randomized.
- 5.2.3 The participant will be instructed to take one (1) tablet of study agent by mouth daily with a meal at about the same time each day. The tablet must be taken whole and should not be chewed, cut, opened or crushed.
- 5.2.4 If the participant is having an end of study follow-up PET-CT scan, they should be instructed to take their dose of agent with the last full meal allowed prior to the scan.
- 5.2.5 The final dose of study agent will be taken on the day prior to the participant's day 11-22 surgery or pre-non-surgical treatment biopsy.

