8. The final dose of study agent will be timed to allow for collection of a PK trough level. The participant will be instructed to take their final dose of study agent as close to 24 hours (no more than 26 hours) prior to the collection of their end-of-study PK sample as possible.
9. FDG-PET/CT: Skull base to thigh. To be performed only on those participants who have had a standard of care staging FDG-PET/CT performed prior to starting study intervention. The participant must have completed a minimum of 10 days of study agent dosing prior to conducting the end of study FDG-PET/CT scan. The scan will be scheduled as close as possible to the date the end of study tissue biopsies are collected.
10. At this contact, the participant will be reminded that their final dose of study agent will be timed against the anticipated time of the End of Study Visit blood draw.
11. This contact will be made 2-72 hours prior to the participant's final day of study agent dosing to remind the participant what time they should take their final dose so that it occurs as close as possible to 24 hours (without going over 26 hours) prior to anticipated time of their End of Study Visit blood draw.

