### 7.3 Evaluation During Study Intervention

#### 7.3.1 Interim Phone Contact

The participant will be contacted on day 5-7 to assess for adverse events and study agent dosing compliance. Adverse Events will be documented on the Adverse Event Worksheet (provided by the CLO at study initiation). The participant will be asked if they have experienced any symptoms or events since the date they signed informed consent for the study. For each event reported document the participant's verbatim description of the event, date reported, onset and end dates, CTCAE v4 term and severity grade, the action taken, outcome, whether the event was a Serious Adverse Event or not, whether the participant dropped from the study due to the event, and the MD's assessment of attribution of the event to the study agent. At this contact, the Concomitant Medication Worksheet will also be reviewed and updated. The participant will be reminded to report any new medications prior to taking them to ensure they are not contraindicated.

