#### 7.3.2 Final Dosing Reminder Call

There are several criteria to be taken into account when determining when the participant should take their final dose of study agent.

- The participant must take study agent for a minimum of 10 days.
- The participant must not take a dose of study agent on the day their end-of-study tissue samples are collected.
- The end-of-study PK sample must be drawn approximately 24 hours but no more than 26 hours after the participant takes their final dose of study agent.
- The study agent must be taken with a meal. However, participants are instructed not to eat or drink anything for 6 or more hours prior to their PET/CT scan.

Therefore, depending on whether or not the participant is having an end of study PET/CT scan and when that scan will occur, in some cases the final dose of study agent will need to be taken and the end-of-study blood samples will need to be collected prior to the PET-CT unless there is sufficient time for the participant to take a dose of study agent after their PET-CT but 24 hours prior to collecting the PK sample on the day of the end-of-study biopsy or surgery. The date and time the participant takes their final dose of study agent will be documented.

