#### 7.4.3 Collection of Blood Samples for Clinical Safety and Research

The following end of study blood samples will be collected:

- A CBC with differential and comprehensive metabolic panel (using the institution's clinical lab supplies and policies/procedures for obtaining these samples).
- Blood for pioglitazone trough levels: Supplies for the collection and storage of plasma for pioglitazone analysis will be provided by the University of Wisconsin's CP Lab. To obtain an accurate pioglitazone trough level, the participant should be instructed to take their final dose of study agent approximately 24 hours (but no more than 26 hours) prior to when this blood sample will be obtained. It is imperative that the date and time of the last dose of study agent is accurately documented in the Visit Guide for this study visit. Instructions for the collection, processing, storage and shipping of research blood and tissue samples are in sections 10.2 and 10.3 of this protocol.

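### During dosing, staff are scheduled to ask about adverse events and new medicines only at Day 5-7; adding the questions to the Final Dose Reminder Call is a cheap, modest safety gain

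*Combined protocol and SAP*

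**What the plan says.** Section 5.7.2.3 provides for one contact of this kind: "Each participant will receive an interim phone contact between their baseline and end of study visits to assess for adverse events". Section 7.3.1 sets the on-treatment enquiry: "The participant will be contacted on day 5-7 to assess for adverse events and study agent dosing compliance". Concomitant medications are reviewed on the same call. After baseline, the schedule of events (7.1) marks both rows only there and at End of Study or Early Termination.

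Section 5.2.5 fixes the end of dosing: "The final dose of study agent will be taken on the day prior to" the end-of-study surgery or biopsy. For anyone who completes dosing, the second enquiry therefore follows the last dose.

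A second call is already planned. The Schema gives "Final Dose Reminder Phone Contact: 12-72 hours prior to the time the participant was instructed to take" the dose before the pioglitazone sample, and section 3 says "The participant will be contacted 12-72 hours prior to this dose time to remind them of the dose timing". Footnote 11 of 7.1 has a different lower limit: "This contact will be made 2-72 hours prior to the" last dosing day. In the schedule this call's column is marked only for dosing and telephone contact, and 7.3.2 discusses only when the final dose should be taken.

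Section 5.6 requires a hold for a related grade 2 event that changes in dose timing or meals do not solve. It requires a stop for related grade 3 events, grade 2 hypoglycemia and jaundice.

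Between the two enquiries the plan relies on the participant. New medicines are to be reported before they are taken (5.5, 7.2.6), and planned contrast scans are to be notified and the dose held (5.4.5). Heart failure and lactic acidosis symptoms are to be reported at once (6.2), and the Pill Diary (Appendix B) lists nine entries that call for immediate contact.

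**The concern.** The 5.6 rules work only if staff learn of an event while doses remain. After the Day 5-7 call no section of the protocol has staff ask again until dosing is over, and the diary's comments column is not seen until the end-of-study visit (5.7.2.1). An event volunteered on the reminder call would have to be recorded (11.1.1), but nobody is told to ask for it.

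What is at stake is that a participant who does not volunteer a symptom continues dosing when an existing rule would hold or stop the agent. Staff then first hear of it at the visit where tissue is taken, or at surgery.

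**Working it through.** The plan gives no figure on this point, so the check compares lists and counts days.

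**Self-report coverage.** Section 6.2 names eight symptoms of heart failure and lactic acidosis. Six match the diary list directly: weight gain, dyspnea, edema, myalgia, respiratory distress and abdominal pain. Malaise and somnolence match if read as weakness or tiredness, so coverage is 6-8 of 8. Section 5.6 has 15 hypoglycemia entries, partly overlapping, of which 2-4 are on the diary list. Jaundice and diarrhea are not on it.

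**Present schedule.** For a course of N doses the last dose is on Day N. Dosing days after the Day 5-7 call number N-7 to N-5; the end-of-study enquiry comes one day later.

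**With the reminder call used.** The call falls 0.5-3 days before the final dose (12-72 h). The interval between the two calls then runs from (N-3)-7 to (N-0.5)-5.

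| Course | Dosing days after Day 5-7 call | Days to end-of-study enquiry, now | Days between the two calls, after the fix |
|---|---|---|---|
| N=10 | 3-5 | 4-6 | 0-4.5 |
| N=21 | 14-16 | 15-17 | 11-15.5 |
| N=25 (delayed surgery) | 18-20 | 19-21 | 15-19.5 |

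**Doses still open to a hold.** For a call h hours before the final dose, floor(h/24)+1 doses remain: h=12 gives 1, h=24-47 gives 2, h=48-71 gives 3. Exactly 72 h gives 4 if that day's dose has not been taken. Footnote 11's 2 h gives 1.

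**Notice before end of study**, taking the visit as 24 h after the final dose: 12+24=36 h to 72+24=96 h, or 1.5-4 days. At 2 h it is 2+24=26 h.

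**Scale.** Section 13.3 plans 26 active participants. Hypoglycemia (pooled rate, 6.2): 83/2383=3.48%, and 26 x 0.0348=0.9, about 1. Diarrhea (metformin monotherapy, 6.2): 26 x 0.532=13.8, about 14. Both are upper figures. The first comes from diabetes-drug trials, whereas this trial excludes drug-treated diabetes, prior hypoglycemia and liver disease (4.2.2, 4.2.14, 4.2.12). The second is given without dose or duration, and 2.3.2 describes the diarrhea as transient. The share that would be grade 2 or worse, ongoing and unreported at the call is not given.

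**Effect of a hold on evaluability.** Section 7.3.2 says "The participant must take study agent for a minimum of 10 days", read here as ten doses taken, and 5.7.1 sets compliance at 80%.
- One dose held of 10 leaves 9: 90% compliant, but below the minimum.
- Three doses held leave 7/10=70%, 11/14=79%, 12/15=80% and 18/21=86%. Courses of 10-14 doses fall below 80%.
- At least ten doses remain after three are held only if N is 13 or more, so courses of 10-12 doses miss the minimum.

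**The case against.** The strongest reply is that this is a deliberate choice and not an error. Sections 5.7.2.3, 7.1 and 7.3.1 agree on one interim call, and 4.4 explains that it replaces a visit. The course is short and the drug is marketed. Entry criteria remove much of the risk: liver disease, prior hypoglycemia and drug-treated diabetes are excluded, and bilirubin and transaminases are capped (4.1.9). Section 2.3.2 adds that metformin used as labeled does not cause hypoglycemia. Diarrhea has no rule of its own in 5.6. All of this stands, and it shrinks the gain. It does not supply an enquiry before the last doses.

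The available text also has limits. The consent pages were removed, and the Visit Guides that structure each contact (12.3) are not shown, so participants or staff may have instructions beyond those seen here. The point is confined to what the protocol sections state.

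A third objection is that the change reaches only the last few doses and leaves most of the mid-course interval. That is correct, and it is why the point is rated low.

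A reader might go further and infer that participants are unmonitored between contacts. The documents do not support that: the self-report routes are explicit, and section 6.2 requires the agent to be stopped and the participant evaluated when heart failure or lactic acidosis symptoms are reported or found.

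**Conclusion.** The concern holds as a cheap improvement of low severity. The scheduled enquiries fall at Day 5-7 and after the last dose, the call between them does not ask, and the self-report list leaves out some triggers of the protocol's own hold and stop rules. Using that call would let the rules act on the last 1-3 doses and give staff about 1.5-4 days' notice before end of study.

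This assumes that the call is made 12-72 h before the final dose and that the participant has an ongoing event not yet volunteered. How often that occurs cannot be derived. A reader might take about 1 and about 14 of 26 as the numbers who would benefit. They are not: they are upper figures for any such event at any time, from other populations or without dose and duration.

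Nor does the point show that a trial comparison is compromised. Section 7.4.5 still asks at end of study about events since consent, so what changes is when staff learn of an event. No efficacy comparison changes, and an earlier drug or contrast exposure would not be prevented.

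**What to change.** In 7.1, mark Adverse Events and Concomitant Medications under the Final Dose Reminder Call. In 7.3.2 and 5.7.2.3, state that the 7.3.1 questions are asked on that call. No dose, hold or stop rule changes.

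The direct cost is a few minutes on a call already made to each of about 39 participants, with no new visit, staff or procedure. The indirect cost arises only where an existing 5.6 rule then requires a hold:
- The last doses are lost. If the final dose is among them, so is the trough, because 7.4.3 has participants "take their final dose of study agent approximately 24 hours (but no more than 26 hours) prior to" the blood draw.
- A short course may miss the 10-day minimum or 80% compliance, as computed above.
- A biopsy delayed to Day 23-26 may fail the condition that dosing continue to the day before sampling (7.4.7). After delayed surgery, section 3 also requires the final dose within 26 h of tissue collection. The plan allows for three unevaluable participants (39-36=3).

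These losses follow from safety rules already in the plan. Where 5.6 stops the agent, the participant is still followed and biopsied if willing, and 13.6 keeps evaluable paired samples in the biomarker analysis.

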#### 5.7.2.4 Pioglitazone analysis:

Blood samples will be collected at the baseline and end of study visits to measure pioglitazone concentration.

## 6. PHARMACEUTICAL INFORMATION

### 6.1 ACTOplus met® XR IND Exempt (132630)

ACTOplus met® XR (Takeda Pharmaceuticals America, Inc., Deerfield, IL) is a fixed-dose combination (FDC) drug of pioglitazone immediate-release combined with metformin extended-release. This FDC is approved as an adjunct to diet and exercise to improve glycemic control for patients with type 2 diabetes mellitus. Pioglitazone is an agonist of peroxisome proliferator-activated receptor  $\gamma$  (PPAR $\gamma$ ), a ligand-activated nuclear transcription factor belonging to the steroid receptor superfamily that is a key regulator of insulin-responsive genes involved in the control of glucose and lipid metabolism as well as adipogenic differentiation. While originally believed to be adipocyte-specific, accumulating data show that PPAR $\gamma$  is also expressed in normal liver and skeletal muscle and in neoplastic tissue, including breast, colon, prostate, and lung. PPAR $\gamma$  activation by pioglitazone in breast, colon, and lung cancer cell lines leads to differentiation and/or apoptosis [16-18; 21]. Consistent with the cell observations, mouse xenograft studies using breast and colon cancer cell lines have shown significant reduction in tumor size after treatment with pioglitazone compared with vehicle controls, with induction of apoptosis in the breast tumors [17; 18]. Pioglitazone was also effective in multiple different carcinogen-induced cancer models, such as colon, lung, and oral squamous cell carcinoma [22; 23; 25; 54].

Metformin, a first-line drug commonly used to treat diabetes mellitus, also inhibits cell growth. Besides inhibiting gluconeogenesis, this biguanide derivative indirectly activates adenosine monophosphate-activated protein kinase (AMPK) in cells by a liver kinase B1 (LKB1)-dependent mechanism. AMPK appears to be a key molecular target for cancers associated with diabetes mellitus and obesity since it is activated under conditions of decreased energy, such as low glucose, hypoxia, or ischemia [28; 29]. Activation of AMPK inhibits mammalian target of rapamycin (mTOR) via tuberous sclerosis complex 2/1. Exposure of breast cancer cells to metformin decreases phosphorylated AKT and activation of

mTOR, resulting in inhibition of cell proliferation and an increase in apoptosis [30]. Metformin also has indirect anti-proliferative effects related to lower systemic levels of insulin.

An NCI, DCP-sponsored nonclinical study evaluated the combination of metformin and pioglitazone for synergistic or additive effects in cancer prevention. In a benzo[*a*]pyrene-induced lung carcinogenesis model, mice were administered metformin (850 mg/kg-bw/day), pioglitazone (15 mg/kg-bw/day), or the combination (same doses) for nine weeks after the last carcinogen dose, with animal sacrifice seven weeks later. Metformin alone caused a 37% reduction ( $p < 0.01$ ) in tumor multiplicity compared with control treatment, whereas pioglitazone alone resulted in a 17% reduction (non-significant) [52]. The metformin plus pioglitazone combination reduced tumor multiplicity by 44% compared with control treatment, suggesting that the two agents work together to reduce tumor multiplicity.

The formulated drug product, ACTOplus met® XR, contains 30 mg pioglitazone and 1000 mg metformin hydrochloride, along with the following inactive excipients: candelilla wax, cellulose acetate, povidone, hydroxypropyl cellulose, lactose monohydrate, magnesium stearate, hypromellose, polyethylene glycols (PEG 400, PEG 8000), sodium lauryl sulfate, titanium dioxide, and triacetin. The tablet consists of an extended-release, osmotically-active core of metformin surrounded by a semipermeable membrane and coated with a pioglitazone drug layer. Two laser-drilled exit ports exist in the membrane, one on either side of the tablet. The semipermeable membrane is permeable to water but not to higher molecular weight components of biological fluids. Upon ingestion, the pioglitazone layer is dissolved; water is then taken up through the membrane, which in turn dissolves the metformin core and excipients, which exit through the laser-drilled ports in the membrane. The rate of drug delivery is constant and dependent upon the maintenance of a constant osmotic gradient across the membrane. The membrane coating remains intact during the transit of the dosage form through the gastrointestinal tract, and is excreted in the feces.

Matching placebo tablets will be manufactured containing lactose monohydrate, microcrystalline cellulose, croscarmellose sodium and magnesium stearate.

